11.2 Severity Assessment

For all AEs occurring during the clinical trial, the Investigator is to classify and report the intensity of AEs using the following definitions as a guideline:

- Mild: awareness of signs and symptoms, but easily tolerated
- Moderate: discomfort, enough to cause interference with usual activity
- Severe: incapacitating, with inability to work or perform usual activity.

11.3 Causality Assessment

The Investigator is to assess the causal relationship (causality) between an adverse event and the investigational product and/or the clinical trial procedure according to the following definitions (Decision of 25 November 2013 on Guideline on Annex I to Regulation (EC) No 1223/2009 (2013/674/EU) - Causality assessment of undesirable effect caused by cosmetic products):

- Very likely
- Likely
- Not clearly attributable
- Unlikely
- Excluded

Medical judgment should be used to determine the relationship, considering all relevant factors including the pattern of reaction, temporal relationships, positive de-challenge or re-challenge, relevant medical history, and confounding factors such as co-medication or concurrent diseases.

Protocol Version 2:

This document contains confidential, proprietary information.

Protocol GLI.04.US.SL.015

CONFIDENTIAL

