7. STUDY TREATMENT

The term “study treatment” refers to the study products (HA Fillers, see Section 7.1)

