7.3 Study Product Accountability

Upon receipt of the study products, the investigator or designee will conduct an inventory. In accordance with federal regulations, the investigator must agree to keep all test article in a secure location with restricted access. Designated study personnel will provide the test article to the subjects in accordance with the protocol.

During the study, the investigator must maintain records of study treatment dispensation and collection for each subject. This record must be made available to the study monitor for the purposes of verifying the accounting of clinical supplies. Any discrepancies and/or deficiencies between the observed disposition and the written account must be recorded along with an explanation. At the conclusion of the study, the investigator will be responsible for returning all unused study product (i.e., Restylane® Contour) unless otherwise instructed by the Sponsor. Shipping label and cost will be provided to the investigator by the Sponsor.

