11.1 Definitions

11.1.1. Adverse Events (AE)

An adverse event (AE) is defined as any untoward medical occurrence in a subject taking part in the clinical study, and which does not necessarily require a causal relationship with the investigational product and/or a clinical trial procedure.

An AE can be any unfavourable and unintended sign (including an abnormal laboratory value), symptom, or disease temporally associated with the use of the investigational product, whether or not related to this product.

When an AE has a likely or very likely causal relationship with the investigational product and/or a clinical trial procedure, it is named undesirable effect or related AE (see Section 3).

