11.1.3. Serious Adverse Events (SAE) and serious undesirable effect/related SAE

A Serious Adverse Event (SAE) is any adverse event which results in death, is life-threatening, requires inpatient hospitalization or prolongation of existing hospitalization, results in persistent or significant disability/incapacity, or is a congenital anomaly/birth defect.

Notes:

The term “immediate vital risk” refers to an event in which the subject was at risk of death at the time of the event; it does not refer to an event that hypothetically might have caused death if it was more severe.

Inpatient hospitalization is considered to have occurred if the subject has had to stay for a night at the hospital. Hospitalization solely for the purpose of a diagnostic test (even if related to an AE), elective hospitalization for an intervention that was already planned before subject enrolment in the clinical trial, admission to a day-care facility, social admission (e.g., if the subject has no place to sleep), or administrative admission (e.g., for a yearly examination) should not be considered as a SAE.

A serious undesirable effect/related SAE is defined as any SAE which the Investigator classifies as having a reasonable possibility for a causal relationship with the investigational product and/or the clinical trial procedure.

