11.4.1. Management and reporting procedures for undesirable effects (i.e. related adverse events)

Undesirable effects should be recorded in the CRF and summarized in the report in a summary table with at minimum the subject number, AE number, AE diagnosis or signs and symptoms, location, date of onset, seriousness, severity, action taken, relationship, date of resolution and concomitant treatment associated as well as a detailed narrative of the event.

In addition, based on his/her medical judgment, the Investigator will assess whether an undesirable effect requires immediate (i.e. within 24 hours) reporting to the Sponsor. In such cases, the summary table will be sent to the Sponsor, along with the AE narrative and any other relevant information (concomitant treatments, product weighing, ...).

All undesirable effects should be appropriately documented, i.e. any relevant information such as demographics, medical history and concomitant therapies should be recorded in the CRF.

The Investigator is to monitor and record the progress of the adverse effect until the last subject's study visit.

The Investigator is to update the AE narrative as appropriate, each time follow-up information is collected and when the final outcome of the adverse effect is known.

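### Adverse-event causality is rated jointly against product and procedure, side is not required for every event, and no adverse-event summary by filler is planned, although each cheek carries a different filler

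*Combined protocol and SAP*

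**What the plan says.** Section 11.3 has the investigator assess the "causal relationship (causality) between an adverse event and the investigational product and/or the clinical trial procedure", with five answers running from very likely to excluded. Section 11.1.1 calls an event an undesirable effect, or related event, when it has a "likely or very likely causal relationship with the investigational product and/or a clinical trial procedure". Section 11.1.3 defines a related serious event as one "having a reasonable possibility for a causal relationship with the investigational product and/or the clinical trial procedure". The threshold wording differs between these two definitions, but the target is the same: product and procedure together, with the product in the singular.

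For undesirable effects, Section 11.4.1 sets a minimum content for the summary table that includes "AE diagnosis or signs and symptoms, location, date of onset, seriousness, severity, action taken, relationship, date of resolution", plus a narrative. Relationship appears once in that list, and neither the filler nor the injection procedure has its own item.

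Section 8.1.1 assigns a treatment to each side of the face from the randomization list and records the amount used in each cheek. Section 7 counts both fillers as study treatment, and Section 7.1 labels both as study products. Section 10 plans treatment comparisons for aggregate size and 3D volume change only. It contains no adverse-event summary.

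**The concern.** The safety section reads as if each subject had one product. Here the subject carries two, and the local reactions of interest can come from either gel or from the act of injecting. A rating that joins product and procedure answers whether the event is related to the study at all. It does not say what the event is related to.

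What is at stake is attribution. When local reactions are reported, a reader will want to know which cheek they occurred in, how severe they were and how long they lasted there, and whether the investigator blamed the filler or the needle. If these items are not collected during the study, they may not be recoverable afterwards. The within-subject design would otherwise supply them cheaply.

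**Working it through.** The plan gives no figure on this point, so there is nothing to reproduce. The check is to follow each kind of event through the recording rules.

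1. **One-sided local event rated likely or very likely.** It is an undesirable effect under Section 11.1.1, so Section 11.4.1 requires a location. If the entry names the cheek, the randomization in Section 8.1.1 gives the filler. The filler can be identified. The relationship item does not show whether the gel or the injection was blamed.

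2. **One-sided local event rated lower.** The scale has five levels. Two of them (very likely, likely) make an event an undesirable effect, which leaves 5 − 2 = 3 levels (not clearly attributable, unlikely, excluded) outside the Section 11.4.1 table. No passage requires a side or location for these.

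3. **Bilateral local event**, such as swelling of both cheeks. The field list gives each event one severity, one relationship and one resolution date. The text neither requires nor forbids separate left and right entries. If the event is entered once, severity and duration by cheek are not held in any tabulated field.

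4. **Event with no location on the face.** Side cannot help here, and the rating remains joint.

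Next, could a simple left-versus-right comparison replace separate ratings? Section 7.5 holds the type of tool (needle or cannula) constant within a subject, which helps. It does not require the same gauge or length on both sides, and it expects the injected volume to differ between sides. Section 7.1 shows each product supplied with its own needles, and Section 8.1.2 allows a touch-up with the amount recorded for the cheek concerned. The injection burden can therefore differ between cheeks, and a raw difference in related events may reflect gel or procedure.

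Finally, does another instrument fill the gap? Section 11.1.2 mentions tolerability scales or a diary and points to an appendix, but its heading limits it to cosmetic safety studies. The only appendix is the self-assessment questionnaire. That asks about each side, but about appearance, feel and preference, and it has no tolerability scale.

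**The case against.** The strongest reply is that much of the information is already there. Location and a narrative are required for every undesirable effect, and side maps to filler through the randomization. A reader might infer from the joint rating that reactions cannot be compared between the two cheeks. The documents do not support that: one-sided related events can be compared whenever the side is entered.

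A reader might also infer that a needle bruise and a gel reaction become indistinguishable. They do not, because the table also records the diagnosis or signs. Only the relationship rating could be the same for both.

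A third tempting reading is that Section 7.3, in asking for "returning all unused study product (i.e., Restylane® Contour) unless otherwise instructed by the Sponsor", removes the comparator from the safety definitions. That sentence concerns the return of stock, and Section 7.2 says the sponsor supplies only that product. It does not define the investigational product for Section 11. The term is loose, not shown to be restrictive.

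One could try to size the loss with assumed rates. If 30% of cheeks had a procedure reaction and, independently, 20% versus 0% had a gel reaction, the joint related rates would be 1 − 0.7 × 0.8 = 44% versus 30%, so a 20-point difference would show as 14. At 60% they would be 1 − 0.4 × 0.8 = 68% versus 60%, or 8 points. These rates are not in the documents, and the plan never makes such a pooled comparison, so they do not measure a loss in this trial.

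Two further points stand. The adverse-event page of the case report form is not in the documents and may already hold a side field or separate ratings. And the study objective in Section 5.1 is ultrasound aggregation and visualization, with no comparative safety aim.

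**Conclusion.** The point holds in a limited form and is minor. Four gaps remain:

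- The relationship rating, as the protocol words it, cannot separate gel reactions from injection reactions.
- Side is required only as an undefined location, and only for the top two of the five causality levels.
- Nothing requires a bilateral local event to be split by cheek.
- Section 10 plans no adverse-event summary by product.

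The size cannot be stated as a number, because the documents contain no adverse-event rates and no planned safety comparison. The conclusion rests on the protocol text alone and assumes that the unseen form asks for no more than the protocol's listed minimum. If the form already has these fields, only the text and the planned listing need changing.

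**What to change.** In Section 11.3 and on the adverse-event page:

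- Record side (left, right, not localised) for every adverse event, whatever its causality rating.
- Enter a bilateral local event once per cheek, each entry with its own severity and dates.
- Rate causality separately for the filler in that cheek and for the injection procedure.
- State that the investigational product means both fillers, and carry this into Sections 11.1.1 and 11.1.3.

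In Section 11.4.1 and Section 10, add a listing of adverse events by product within subject, showing the two causality ratings side by side.

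The cost is a few form fields, one listing and slightly more data entry, with no new visit or procedure. There is one drawback. The synopsis describes only the subject as blinded, and no section describes the investigator as blinded, so the filler-versus-procedure rating would rest on the judgement of someone who may know which product is in each cheek. The listing should therefore be descriptive only, with no test between products.

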11.4 Collection, Management and Reporting Procedures

The period of collection of adverse events starts from the time of signature of the Informed Consent Form (ICF) by the subject (*and/or, for subjects who are minor, by the parents/legal representatives*) until the end of the subject's participation in the clinical study.

If a Serious Adverse Event (SAE) is on-going at the final clinical trial visit, it should be followed by the Investigator until it has resolved or has reached a stable condition.

After the subject completes the clinical study, the Investigator should also inform the Sponsor (see Sponsor's contact details below) if he/she becomes aware of an SAE involving a subject who has participated in the clinical study.

At each post-enrollment visit, the Investigator will question the subject about AEs using an open non-persuasive question to elicit reporting of AEs, for example "*Have you noticed any change in your health since the last visit?*" Direct questioning and examination will be performed when appropriate.

The Investigator will obtain and maintain in the subject's files all pertinent medical records, and (if applicable) information and medical judgment from colleagues who assisted in the treatment and follow-up of the subject. If necessary, the Investigator will contact the subject's personal physician or hospital staff to obtain further details.

As a minimum, Investigators are requested to report in the Case Report Form (CRF) and in the report all related adverse events (i.e. undesirable effects) and all Serious Adverse Events, whether related or not.

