11. ADVERSE EVENTS

Throughout the course of the study, all adverse events will be monitored and reported on an adverse event CRF/eCRF without omitting any requested and known information. When AEs occur, the main concern is the safety of the study subjects. At time of the informed consent signature, each subject must be given the name and phone number of investigational site personnel for reporting AEs and medical emergencies.

At each visit, after the subject has had the opportunity to spontaneously mention any problems, the investigator should inquire about AEs by asking the standard questions:

- “Have you had any health problems since your last study visit?”
- “Have there been any changes in the medicines you take since your last study visit?”

AEs should be reported for any clinically relevant change, as determined by the Investigator, in concomitant medication(s) that is the result of an untoward (unfavorable and unintended) change from baseline in a subject’s medical health following exposure to the study treatment.

Changes from baseline in any protocol-specific parameter evaluated during the study are to be reviewed by the Investigator. In addition, the subject’s responses to any questionnaire utilized during the study are to be reviewed by the investigator. Any untoward (unfavorable and unintended) change from baseline in a protocol-specific parameter or question response that is clinically relevant, in the opinion of the investigator, is to be reported as an AE. These clinically relevant changes will be reported regardless of causality.

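### The stated minimum for adverse event reporting in 11.4 is narrower than Section 11 requires for the CRF, and nothing wider governs the study report, so non-serious events not rated likely or very likely related need not appear there

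*Combined protocol and SAP*

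**What the plan says.** **What goes on the CRF.** The opening of Section 11 states that "all adverse events will be monitored and reported on an adverse event CRF/eCRF without omitting any requested and known information". For untoward changes in study parameters or questionnaire answers that the investigator judges clinically relevant, it adds: "These clinically relevant changes will be reported regardless of causality". Other sections agree. The visit steps (8.1.1 step 10; 8.1.2 and 8.1.3, step 1) have AEs recorded with no causality condition, 11.2 has intensity graded for every AE, and 13.2 asks for thorough documentation of all of them.

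**The stated minimum.** Section 11.4 says "As a minimum, Investigators are requested to report in the Case Report Form (CRF) and in the report all related adverse events", which it equates with undesirable effects, and "all Serious Adverse Events, whether related or not". This floor covers both the CRF and the report.

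**What related means.** For an AE, 11.1.1 requires a "likely or very likely causal relationship with the investigational product and/or a clinical trial procedure, it is named undesirable effect or related AE". For a serious AE, 11.1.3 asks instead whether the investigator sees the event as "having a reasonable possibility for a causal relationship with the investigational product and/or the clinical trial procedure". Section 11.3 lists five causality levels: *Very likely*, *Likely*, *Not clearly attributable*, *Unlikely* and *Excluded*. It does not say which of them meet the 11.1.3 wording. Section 11.1.1 sends the reader to Section 3 for the term, but Section 3 defines neither related nor undesirable effect.

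**What goes in the report.** The summary table in 11.4.1 is for undesirable effects. Its minimum contents include "AE diagnosis or signs and symptoms, location, date of onset, seriousness, severity, action taken, relationship". Neither side of face nor assigned filler is named. Section 10 specifies no AE summary.

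**The concern.** A protocol that asks for all AEs in one place and states a smaller sufficient set in another invites sites to work to the smaller one, particularly when it sits in the operational section on collection and reporting.

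The dividing line is a causality rating. The synopsis describes the study as blinded for subjects only. The investigator injects both products by assigned side (8.1.1, steps 8 and 9) and rates causality (11.3). With two fillers given in one session, an ambiguous local finding could plausibly be rated *Not clearly attributable*. That rating, if the event is non-serious, takes it outside the stated minimum. At stake is whether the safety description of each filler is complete, and whether its completeness depends on a judgement made with knowledge of the product.

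**Working it through.** The plan gives no figure to reproduce, so the check sets the rules side by side. Inputs: the five causality levels of 11.3, two seriousness levels, the scope in Section 11, the floor in 11.4, and the definition of a related AE in 11.1.1. That makes 5 × 2 = 10 combinations.

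| Causality level | Non-serious: Section 11 (CRF) | Non-serious: 11.4 floor (CRF and report) | Serious: Section 11 (CRF) | Serious: 11.4 floor (CRF and report) |
|---|---|---|---|---|
| Very likely | required | required | required | required |
| Likely | required | required | required | required |
| Not clearly attributable | required | not required | required | required |
| Unlikely | required | not required | required | required |
| Excluded | required | not required | required | required |

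1. Section 11 requires 10 of 10 on the CRF.
2. The 11.4 floor requires 5 serious + 2 non-serious = 7 of 10.
3. The gap is 10 − 7 = 3 combinations, all non-serious.

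**Does the second definition of related matter to the count?** Section 11.1.3 applies only to serious events, and 11.4 takes all of those regardless of relationship. Its wording therefore changes the count by 0. If the 11.1.3 wording were extended to non-serious events and read to include *Not clearly attributable* (an assumption; the documents do not say so), the floor would be 5 + 3 = 8 of 10, still 2 short of Section 11.

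**CRF versus report.** For the CRF, the floor sits below a broader rule that still applies. For the report, Section 11 is silent. The applicable text is 11.4 and 11.4.1, and both stop at related events, plus serious ones in 11.4. A complete CRF would still not oblige anyone to show the three missing combinations in the report.

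**Scale.** The documents give no expected AE rate and no basis for the number of omissions. As an illustration only, with 15 subjects (the completer target in 6.1):

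- One more subject with an event moves a filler's rate by 1/15 = 6.7 percentage points.
- Zero events in 15 gives a one-sided 95% upper limit of 1 − 0.05^(1/15) = 0.181, about 18%.

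These figures hold for any 15-subject study. They do not measure this defect. The injected number may exceed 15, because 6.1 sets 15 as a minimum for enrolment, and a second event in a subject already counted would not move a subject-level rate.

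**The case against.** The strongest reply is that 11.4 is worded as a floor. A site that records everything satisfies both sections, and several other passages ask for full capture. That is correct for the CRF: there is no strict contradiction, and 11.4 cannot override Section 11. What remains is that the protocol presents as sufficient a set that breaches its own rule. The reply does not help the report, where no broader rule exists.

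A reader might go further than the documents allow in four ways.

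- *The two definitions of related cause events to be dropped.* They do not, as the zero change above shows. The omission comes from the 11.1.1 threshold combined with the 11.4 floor. The double definition is a separate defect of clarity.
- *An omitted event is lost for good.* Section 13.2 requires source documentation and allows later CRF additions, including for AEs, and 13.1 provides for monitoring against source. Recovery is possible, though not assured.
- *A planned safety comparison of the fillers is biased.* None is planned. The synopsis and Section 10 compare aggregation, volume change and the questionnaire.
- *The filler responsible for a local event cannot be identified.* The 11.4.1 list is itself a minimum and includes subject number and location. If location is recorded with side, the randomization list gives the filler. The weakness is only that side is not explicitly required.

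It can also be said that a clinically relevant lump or asymmetry would often show up in imaging or the questionnaire, and so be reported as an AE whatever its cause. That stands for the CRF and for changes the investigator judges clinically relevant, but it does not bring the event into the report. Section 11.1.2 does send local tolerability signs to the final report. However, its heading limits it to cosmetic safety studies, and the visit schedule contains no tolerability scale or diary, so it does not clearly close the gap.

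**Conclusion.** The concern holds as an inconsistency of scope. Three of the 10 combinations of seriousness and causality are required on the CRF by Section 11 but lie outside the 11.4 minimum, and the same three need not appear in the study report under any clear rule. The report gap matters more, because complete data capture does not cure it. The unmapped double wording of related is a lesser, separate fault that removes no event by itself.

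The conclusion rests on three readings: that related in 11.4 carries the 11.1.1 meaning, which 11.4 supports by equating it with undesirable effects; that the investigator knows the side assignment, which follows from subject-only blinding and the injection steps; and that no CRF instruction outside these documents sets a wider scope. The size of any effect on the reported event rates is unknown.

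**What to change.** - Align the minimum sentence in 11.4, and the table in 11.4.1, with Section 11, so that every AE goes on the CRF and is listed in the report whatever its causality rating.
- Use one definition of related for serious and non-serious events, mapped to the five levels in 11.3, and correct the pointer to Section 3. Which side of the line *Not clearly attributable* falls on is for the sponsor to decide; the documents do not settle it.
- Require side of face for local events, which gives the assigned filler.
- State in Section 10 that AEs will be listed by filler for all injected subjects, not only completers.

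Rating causality separately for each filler would be an optional refinement. The cost is protocol and CRF wording and a listing with a few more minor events.
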